Abbreviations: ADA: anti-drug antibody; AE: adverse event; anti-HBc: hepatitis B core antibody; anti-HBs: antibody to hepatitis B surface antigen; C: cycle; COVID-19: coronavirus disease; CR: complete response; CT: computed tomography; D: day(s); ECG: electrocardiogram; EOI: end of infusion; COVID-19: coronavirus disease; CR: complete response; CT: computed tomography; D: day(s); ECG: electrocardiogram; EOI: end of infusion; COVID-19: coronavirus disease; CR: complete response; CT: computed tomography; D: day(s); ECG: electrocardiogram; EOI: end of infusion; COVID-19: coronavirus disease; CR: complete response; CT: computed tomography; D: day(s); ECG: electrocardiogram; EOI: end of infusion; COVID-19: coronavirus disease; CR: complete response; CT: computed tomography; D: day(s); ECG: electrocardiogram; EOI: end of infusion; COVID-19: coronavirus disease; CR: complete response; CT: computed tomography; D: day(s); ECG: electrocardiogram; EOI: end of infusion; COVID-19: coronavirus disease; CR: complete response; CT: computed tomography; D: day(s); ECG: electrocardiogram; EOI: end of infusion; COVID-19: coronavirus disease; CR: complete response; CT: computed tomography; D: day(s); ECG: electrocardiogram; EOI: end of infusion; COVID-19: coronavirus disease; CR: complete response; CT: complet

; EoS: end of study; EoT: end of treatment; CC

; HbsAg: hepatitis B surface antigen; h: hour; HL: Hodgkin lymphoma; min: minute; PCR: polymerase chain reaction; PD: progressive disease;
 ; PET-CT: positron emission tomography-CT; PF: pediatric short form; PGI-TT: Patient Global Impression of Treatment Tolerability;
 PGIC: Patient Global Impression of Change;
 CCI
 <li

PRO-CTCAE: Patient-Reported Outcomes version of the Common Terminology Criteria for Adverse Events; Q1W: every week; Q3W: every 3 weeks; Q6M: every 6 months; Q6W: every 6 weeks; RECIL: Response Evaluation Criteria in Lymphoma; RT: radiation therapy; SAE: serious adverse event; SF: short form; SOI: start of infusion; TIM-3: T cell immunoglobulin and mucin domain-containing protein-3; V: visit.

	At Disease Progression a	EoT b	Post-treatment Safety Follow-up c		Survival Follow-up c	
Procedure/Visit (Window)		+ 14 D	Day 30 Post Last Dose (± 7 D)	Day 90 Post Last Dose (± 7 D)	Q6M Post Last Disease Assessment (± 14 D)	
Abbreviated (symptom-directed) physical examination including weight (Section 8.2.2)		Х	Х	Х		
12-lead ECG (triplicate) (Section 8.2.4)		X				

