#### Vital Signs

Descriptive statistics will be provided for the vital signs measurements and changes from baseline by scheduled time of evaluation and by treatment part, including the EoT visit as well as for the maximum and minimum post-baseline values.

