- Baseline is the last non-missing value obtained prior to the first dose/administration of any study treatment and any information taken after first dose/administration of study treatment is regarded as post-baseline information. If two visits are equally eligible to assess participant status at baseline (eg. screening and baseline assessments both on the same date prior to first dose/administration with no washout or other intervention in the screening period), the average is taken as the baseline value. For non-numeric laboratory tests (ie, some of the urinalysis parameters) where taking an average is not possible then the best value is taken as baseline as this is the most conservative. In the scenario where there are two assessments on Day 1 prior to first dose, one with time recorded and the other without time recorded, the one with time recorded is selected as baseline. Where safety data are summarized over time, study day is calculated in relation to date of first treatment. For assessments on the day of first dose where time is not captured, a nominal pre-dose indicator, if available, serves as sufficient evidence that the assessment occurred prior to first dose. Assessments on the day of the first dose where neither time nor a nominal pre-dose indicator are captured is considered prior to the first dose if such procedures are required by the protocol to be conducted before the first dose. If no value exists before the first dose/administration, then the baseline value is treated as missing.
- In all summaries, change from baseline endpoints will be calculated as the post-treatment value minus the value at baseline. The percentage change from baseline will be calculated as (post-baseline value baseline value) / baseline value × 100. For any endpoint subjected to log transformation, the change from baseline calculated and summarized on the log scale will be back-transformed and presented as a 'baseline scaled ratio' (BSR). Percentage change will be then calculated as (BSR 1) × 100.
- Unless stated otherwise, two-sided confidence intervals are produced at 95%.

– ed. 3.0

- For the purposes of summarizing safety data assessed at visits, in addition to baseline
 data, only on treatment data will be included in the summary tables. On treatment
 data will be defined as data after the first dose of IP and with assessment date up to
 and including the date of last IP + 90 days, and prior to the start of any subsequent
 cancer therapy.

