3.3.2 Visit Window

For safety and tumor assessments, visit windows are defined for any presentations that summarise values by visit. The following conventions apply:

For tumor assessments:

 The protocol assigned windows for tumor assessments will be used to assign the result to a particular visit.

For safety assessments:

- Visit windows will be exhaustive so that data recorded at any timepoint has the potential
 to be summarized. Inclusion within the visit window will be based on the actual date and
 not the intended date of the visit.
- All unscheduled visit data have the potential to be included in the summaries.
- The window for the visits following baseline will be constructed in such a way that the
 upper limit of the interval falls half way between the two visits (the lower limit of the
 first post-baseline visit is Day 2). If an even number of days exists between two
 consecutive visits then the upper limit is taken as the midpoint value minus 1 day.
- If treatment cycle delays are experienced, the planned dosing visit windows will be
 modified during the programming to anchor to the actual visit date where intervention
 was administered on to adjust for these treatment cycle delays. The same rules apply to
 safety visits of other types (non-dosing visits) where the safety visit is moved due to a
 treatment cycle delay.
- Visit windowing will be done separately for each assessment based on the schedule of events specific to that assessment. See Appendix B for details.
- For summaries showing the maximum or minimum values, the maximum/minimum value recorded on treatment will be used (regardless of where it falls in an interval).

- Listings should display all values contributing to a time point for a participant.
- For visit based summaries, if there are more than one value per participant within a visit window then the closest value to the scheduled visit date will be summarized, or the earlier, in the event the values are equidistant from the nominal visit date. If there is still a tie, preference to the nominal visit at which the results were reported at will be given. The listings will highlight the value for the participant that contributed to the summary table, wherever feasible. Note: in summaries of extreme values, all post baseline values collected will be used including those collected at unscheduled visits regardless of whether or not the value is closest to the scheduled visit date.

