Appendix B Time windows

B 1 Tumor assessments

Timepoint	Naming convention in outputs	Window
Screening	Screening	-28 – 1
At least 10 days after sabestomig administration in Cycle	CCI	CCI
At least 10 days after sabestomig administration in Cycle	CCI	CCI
At least 10 days after sabestomig administration in Cycle	CCI	CCI
1 year after date of first infusion	After 1 year	314 – 455 [a]
1 year and 6 months after date of first infusion	After 1.5 years	456 – 638 [a]
2 years after date of first infusion	After 2 years	639 – 821 [a]
2.5 years after date of first infusion	After 2.5 years	822 – 913 [a]
Q6M until EoS		

Any scan not within the above windows will be assigned to an unscheduled timepoint.

[a] If there are multiple scans in this period, the earliest scan will be assigned to the timepoint.

B 3 Time windows for Part A

	Window					
Visit	Hematology Chemistry	Physical examination Vital Signs	Coagulation	ECG	B-symptoms	Thyroid function
Cycle 1 Day 1	1	1	1	1	1	1
Cycle 1 Day 3	2-5					
Cycle 1 Day 8	6 - 11	2 - 11	2 - 11	2 - 15		
Cycle 1 Day 15	12 - 18	12 - 18	12 - 18			2 - 18
Cycle 2 Day 1	19 - 32	19 - 25	19 - 32	16 - 25	2 - 32	19 - 32
Cycle 2 Day 8		26 - 36		26 - 36		
Cycle 3 Day 1	33 - 53	37 - 53	33 - 53	37 - 53	33 - 53	33 - 53
Cycle 4 Day 1	54 - 74	54 - 74	54 - 74	54 - 74	54 - 74	54 - 74
Cycle 5 Day 1	75 - 95	75 - 95	75 - 95	75 - 95	75 - 95	75 - 95

Time windows for Part B B 3

	Window					
Visit	Hematology Chemistry	Physical examination Vital Signs	Coagulation	ECG	B-symptoms	Thyroid function
Cycle 1 Day 1	1	1	1	1	1	1
Cycle 1 Day 8	6 - 11	2 - 11	2 - 11	2 - 15		
Cycle 1 Day 15	12 - 18	12 - 18	12 - 18			2 - 18
Cycle 2 Day 1	19 - 32	19 - 25	19 - 32	16 - 25	2 - 32	19 - 32
Cycle 2 Day 8		26 - 36		26 - 36		
Cycle 3 Day 1	33 - 53	37 - 53	33 - 53	37 - 53	33 - 53	33 - 53
Cycle 4 Day 1	54 - 74	54 - 74	54 - 74	54 - 74	54 - 74	54 - 74
Cycle 5 Day 1	75 - 95	75 - 95	75 - 95	75 - 95	75 - 95	75 - 95

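### Safety visit windows have no end-of-treatment, Day 30 or Day 90 slot, so follow-up values of participants who stop early are tabulated under cycles they never received

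*SAP*

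**What the plan says.** SAP 3.3.2 sets the windowing rule for safety data. Assignment follows the day the assessment was done: "Inclusion within the visit window will be based on the actual date". The windows are meant to leave no gaps: "Visit windows will be exhaustive so that data recorded at any timepoint has the potential" to be summarised. Boundaries lie midway between scheduled visits. One re-anchoring rule is given, and it opens: "If treatment cycle delays are experienced, the planned dosing visit windows will be" modified. The nominal visit matters only as the last tie-break between values already inside the same window.

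SAP 3.3.1 limits by-visit safety tables to baseline and what it calls on-treatment data. That runs from the first dose up to "and including the date of last IP + 90 days", and stops at any new cancer therapy.

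Appendix B gives the safety windows under "Time windows for Part A" and a matching Part B table. Both list Cycle 1 Day 1 to Cycle 5 Day 1 and no follow-up visit.

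Protocol Table 4 schedules vital signs, chemistry and hematology at end of treatment (EoT) and at 30 and 90 days after the last dose (each ±7 days), and ECG at EoT. Protocol 9.4.3.3 wants vital signs summarised by scheduled time, "including the EoT visit as well as for the maximum and minimum post-baseline values". SAP 4.5.6.2 and 4.5.7.2 commit to by-visit summaries of vital signs and ECG. SAP 4.5.4.2 makes the by-visit laboratory change plot optional.

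**The concern.** EoT, Day 30 and Day 90 move with each participant's last dose, while the Appendix B windows are fixed study days counted from the first dose. A rule that uses only the study day cannot recognise a follow-up visit. It gives the value the label of whichever cycle would have been due then.

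Later cycle rows would then combine participants still being dosed with participants who have stopped, often for toxicity or progression, and the label would say that all of them reached that cycle. Changes in vital signs, laboratory values and ECG are among the primary safety endpoints, and a by-visit table is where a reader looks for drift over repeated dosing. The EoT vital-sign summary that the protocol names also has no window to fill it.

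**Working it through.** **Reproducing the plan's windows.** Inputs: the 21-day cycle (Cycle k Day 1 is study day 1 + 21(k−1)), the visit days in protocol Tables 2 and 3, and the midpoint rule of SAP 3.3.2. Example: Cycle 3 Day 1 is Day 43 and Cycle 4 Day 1 is Day 64. Twenty days lie between them, an even number, so the limit is the midpoint 53.5 rounded up, minus 1, which is Day 53, as stated. Of 41 post-baseline windows checked (six Part A columns plus Part B hematology/chemistry), 40 reproduce. The exception is Part B hematology/chemistry at Cycle 1 Day 8: stated as Days 6–11, while the rule gives 2–11 because Part B has no Day 3 visit.

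**Placing the follow-up visits.** Let L be the study day of the last dose, with dosing on schedule. The Day 30 visit spans L+23 to L+37 (15 days). The Day 90 visit spans L+83 to L+97, but the 90-day cap keeps only L+83 to L+90 (8 of 15 days).

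| Doses | L | Day 30 visit | Laboratory window (days of 15) | Day 90 days kept | Window |
|---|---|---|---|---|---|
| 1 | 1 | 24–38 | C2D1 (9), C3D1 (6) | 84–91 | C5D1 |
| 2 | 22 | 45–59 | C3D1 (9), C4D1 (6) | 105–112 | C6D1* |
| 3 | 43 | 66–80 | C4D1 (9), C5D1 (6) | 126–133 | C7D1* |
| 4 | 64 | 87–101 | C5D1 (9), C6D1* (6) | 147–154 | C8D1* |

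C2D1 stands for Cycle 2 Day 1, and so on. *Not listed in Appendix B; obtained by extending the rule.

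Vital signs differ in one cell. After one dose, the Day 30 visit falls in C2D1 (19–25) on 2 days, in C2D8 (26–36) on 11 and in C3D1 (37–53) on 2. A participant who has stopped has no dosing-visit value in these windows to displace the follow-up value.

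**Illustrative size.** Assumptions: a share q stops after each of doses 1 to 4, dosing is on schedule, visits are spread evenly over their windows, and no new therapy starts before the visit. EoT values are not counted.

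- C5D1: still dosed, 1 − 4q. Follow-up values, (8/15 + 6/15 + 9/15)q = (23/15)q = 1.53q. Share = 1.53q / (1 − 4q + 1.53q). For q = 5%: 0.0767/0.8767 = 9%. For 10%: 0.1533/0.7533 = 20%. For 15%: 0.23/0.63 = 37%.
- C4D1: still dosed, 1 − 3q. Follow-up values, (6/15 + 9/15)q = q. Share = q / (1 − 2q): 6%, 13% and 21%.

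The C4D1 and C5D1 windows are the same for vital signs, which Table 4 schedules at the same follow-up visits, so the same fractions apply there. If new therapy starts first, the values are excluded and the shares fall.

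**The case against.** The strongest reply is that Appendix B is only a sketch. It ends at Cycle 5 Day 1 although treatment may run to 35 cycles, its section labels run B 1, B 3, B 3, and SAP 3.3.2 says windows follow the schedule of events for each assessment, which includes Table 4. So follow-up windows are permitted. That is true, but it does not supply them. The midpoint rule cannot place a visit that moves with the last dose unless the SAP names that anchor, and it names none. A programmer who follows the text mislabels the values; one who avoids this must invent a rule.

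Other objections stand and limit the point:

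- A reader might infer that the whole Day 90 visit up to Day 95 enters Cycle 5 Day 1 after one dose. That would make the multiplier 12/15 + 6/15 + 9/15 = 1.8 and the shares 10%, 23% and 40%. The 90-day cap in SAP 3.3.1 ends at Day 91, so these figures are too high.
- A reader might infer that the safety results as a whole are compromised. They are not. Worst-grade, maximum/minimum, adverse event and dose-limiting toxicity outputs do not use these windows, and neither dose escalation nor the Part B safety criteria rest on by-visit means.
- No hematology or chemistry table by cycle is firmly specified in the SAP, although protocol 9.4.3.3 does ask for laboratory values over time.
- A pre-dose cycle value is itself taken 21 days after the previous dose, so a Day 30 value is only 2 to 16 days later (23−21 to 37−21). The Day 90 values are the clearly off-drug ones.
- The EoT summary is not abandoned. The SAP is to be read with the protocol and declares no change to planned analyses. What is missing is the window that would produce it.

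**Conclusion.** The concern holds in limited form. As written, the windowing rule puts follow-up values of early stoppers under visits of cycles they did not receive. The firm effect is on by-visit vital signs and the EoT ECG, with a possible effect on by-visit laboratory change output. The EoT vital-sign summary named in the protocol has no window.

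The placement in the table follows from the documents, given on-schedule dosing. Labels beyond Cycle 5 Day 1 rest on extending the rule. The percentages are illustrations: neither document gives a discontinuation rate, q = 15% would mean that 60% have stopped by the fourth dose, and early new therapy lowers the shares. The documents do not support saying that trends over cycles cannot be read at all. They support saying that later cycle rows would be mixed to an unknown degree. This should be corrected before the tables are programmed, but it does not threaten the trial's decisions.

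**What to change.** In SAP 3.3.2 and Appendix B:

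- Add EoT, Day 30 and Day 90 as analysis visits anchored to the last dose date L. Under the same midpoint rule, Day 30 would run to L+60 and Day 90 from L+61 to the L+90 cap; for L = Day 22, to Day 82 and then Days 83–112. The lower limit of Day 30 needs a stated rule for EoT, which the SAP must supply.
- Let a cycle window accept a value only if that cycle's dose was given, or if the value was taken before the next planned dose date. Send later values to the follow-up visits.
- Show EoT as its own row for vital signs, as protocol 9.4.3.3 requires.
- State how windows continue after Cycle 5 Day 1, and start the Part B hematology/chemistry Cycle 1 Day 8 window at Day 2, so that the windows are exhaustive as SAP 3.3.2 intends.

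The cost is SAP wording and windowing code. No new data are needed.

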3.3.3 Handling of Unscheduled Visits

Refer to Section 3.3.2.

3.3.4 Multiplicity/Multiple Comparisons

Not applicable.

3.3.5 Handling of Protocol Deviations in Study Analysis

Important protocol deviations (IPDs) are those deviations from the protocol likely to have an impact on the perceived efficacy and/or safety of study intervention.

IPDs may include, but are not limited to the following:

- Written informed consent not obtained prior to mandatory study specific procedures, sampling and analyses
- Participants who did not meet inclusion criteria or met exclusion criteria, and received study intervention
- No baseline Lugano assessments on or before the date of first dose
- Participants who received prohibited concomitant medications during study period
- Participants who met study intervention discontinuation criteria but continued study intervention, and potentially had major impact to safety of participants according to clinical judgement

Protocol deviations will be reviewed on a case-by-case basis by AstraZeneca to determine their level of importance. Deviations considered to be important will be listed and discussed in the CSR as appropriate. All decisions on importance will be made ahead of database lock and will be documented as part of the Data Review Meeting minutes prior to the primary analysis being performed.

A detailed list of protocol deviations to be considered are defined in the study specific Protocol Deviation Specifications.

None of the deviations will lead to participants being excluded from any analysis populations described in the SAP, unless otherwise specified. If a deviation is serious enough to have a potential impact on the primary analysis, sensitivity analyses may be performed. The need for such a sensitivity analysis will be determined following review of the protocol deviations ahead of database lock and will be documented prior to the analysis being conducted.

A list of all protocol deviations will be reviewed and decisions regarding how to handle these deviations in the analyses will be documented by the study team physician, clinical pharmacology scientist and statistician prior to database lock.

3.3.6 Missing Dates

When partial dates exist in the data there are some general conventions to be applied when the month or day are missing. These are described in the PHUSE guidance on partial dates, which are outlined below:

If the whole date is missing, it is more difficult to follow a general principle and these are reviewed within the study and decided on how to be handled. General guidance for completely missing dates are provided below, but the guidance is assessed as necessary within the study.

Generally, the imputation of dates is used to decide if an observation is treatment emergent for adverse events (AEs) or concomitant medications. The imputed dates should not be used to calculate durations, where the results would be less accurate.

The following are the guidelines used when partial dates are detected in the study:

- For missing diagnostic dates (eg,: disease diagnosis), if day and/or month are missing use
 01 and/or Jan. If year is missing, put the complete date to missing.
- For missing AE and concomitant medication start dates, the following is applied:
 - a. Missing day impute the 1st of the month unless month is the same as month of the first dose of study drug then impute first dose date.
 - b. Missing day and month impute 1st January unless year is the same as first dose date then impute first dose date.

- c. Completely missing impute first dose date unless the end date suggests it could have started prior to this in which case impute the 1st January of the same year as the end date.
- Imputed start date should be no later than the end date.
- For missing AE and concomitant medication end dates, the following is applied:
 - a. Missing day impute the last day of the month unless both the month and the year are the same as the last dose date or the analysis data cut-off date then impute the last dose date or the analysis data cut-off date.
 - b. Missing day and month impute 31st December unless the year is the same as the last dose date or the analysis data cut-off date then impute the last dose date or the analysis data cut-off date.
 - c. Completely Missing need to look at whether the AE/medication is still ongoing before imputing a date and also when it started in relation to study drug. If the ongoing flag is missing then assume that AE is still present / medication is still being taken (ie, do not impute a date). If the AE/medication has stopped and start date is prior to first dose date then impute first dose date. Or if it started on or after first dose date then impute to the last dose of study drug date + 1.
- Flags are retained in the database indicating where any programmatic imputation has been applied, and in such cases for AEs and concomitant medications, any durations would not be calculated.
- If a participant is known to have died where only a partial death date is available then the
 date of death is imputed as the latest of the last date known to be alive +1 from the
 database and the death date, using the available information provided and applying the
 following:
 - For Missing day only using the 1st of the month.
 - For Missing day and Month using the 1st of January.

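### SAP 3.3.6 compares the month but not the year with the first dose when a start day is missing, so later-year SAEs, AEs after subsequent therapy and late medications can be misclassified

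*SAP*

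**What the plan says.** SAP 3.3.6 (Missing Dates) states that "the imputation of dates is used to decide if an observation is treatment emergent for adverse events (AEs) or concomitant medications". For start dates of AEs and concomitant medications:

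- Start rule a, day missing: impute the first of the month, "unless month is the same as month of the first dose of study drug", in which case impute the first-dose date.
- Start rule b: "Missing day and month impute 1st January unless year is the same as first dose date then impute first dose date".
- Guard: "Imputed start date should be no later than the end date".

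For end dates with the day missing (end rule a), the last day of the month is imputed "unless both the month and the year are the same as the last dose date or the analysis data cut-off date". On durations, "The imputed dates should not be used to calculate durations, where the results would be less accurate".

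The imputed dates feed two classifications:

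- SAP 4.5.2.1 places an AE in the post-treatment phase if it starts more than 90 days after treatment stops, or on or after subsequent anticancer therapy. SAP 4.5.2.2 tabulates treatment-emergent AEs and only lists the others.
- SAP 4.1.8.1 sorts medications into prior, concomitant and post-treatment from the imputed start and stop dates. Post-treatment means a start later than 90 days after the last dose.

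Protocol 8.3.1 collects AEs until 90 days after the last dose and SAEs until the end of the study. Both continue after a new anticancer treatment has begun.

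**The concern.** Start rule a is the only one of the three rules above with no year condition. Start rule b compares the year, and end rule a compares month and year. No other section of the SAP supplies the missing condition.

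A programmer who codes the rule as written would give the first-dose date to any record whose start month has the same name as the first-dose month, in whatever year it fell. A record from a later year is then moved back by about a year or more, into the treatment period. AE and SAE incidence is a primary endpoint in both parts of the study (protocol Table 5, SAP Table 2), and some dose-level groups are very small, so one misplaced SAE could be visible in a table.

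**Working it through.** The plan gives no figure to reproduce. The check applies start rule a as written, then with a year condition added, and compares the resulting status.

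**Inputs.** From the documents: dosing every 3 weeks for at most 35 cycles (protocol 4.1.1, 4.1.2), the 90-day limits (SAP 4.1.8.1, 4.5.2.1), and the end-date guard (SAP 3.3.6). Assumed for illustration: first dose on 15 March 2023, doses exactly 21 days apart, and a start that breaches the guard set equal to the end date.

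**Dates.** The last of k doses falls 21(k − 1) days after the first.

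- 6 doses: 105 days later, 28 June 2023; plus 90 days is 26 September 2023.
- 15 doses: 294 days later, 3 January 2024; plus 90 days is 2 April 2024.
- 35 doses: 714 days later, 26 February 2025.

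| Record (day missing) | Rule as written | With year compared |
|---|---|---|
| SAE Mar 2024, 6 doses | 15 Mar 2023, treatment-emergent | 1 Mar 2024, post-treatment |
| Same SAE, end date 20 Mar 2024 | 15 Mar 2023, treatment-emergent | 1 Mar 2024, post-treatment |
| AE Mar 2024, 15 doses, subsequent therapy 10 Feb 2024 | 15 Mar 2023, treatment-emergent | 1 Mar 2024, post-treatment |
| Medication Mar 2024, ongoing, 6 doses | 15 Mar 2023, concomitant | 1 Mar 2024, post-treatment |
| AE Mar 2024, still on treatment | 15 Mar 2023, treatment-emergent | 1 Mar 2024, treatment-emergent |
| Medication Mar 2021, ongoing | 15 Mar 2023, concomitant | 1 Mar 2021, concomitant |
| Medication Mar 2021, stopped 30 Jun 2021 | 30 Jun 2021, prior | 1 Mar 2021, prior |
| AE Mar 2023, 6 doses | 15 Mar 2023, treatment-emergent | 15 Mar 2023, treatment-emergent |

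The second row shows why the guard does not help. It blocks only a start later than the end, and the error moves the start earlier.

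**Range of exposure for late SAEs.** Without subsequent therapy, the two readings differ when the days from first dose to the correctly imputed date exceed 21(k − 1) + 90.

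- One year later (1 March 2024): 352 days. 352 − 90 = 262 and 262/21 = 12.5, so k − 1 ≤ 12 and status is wrong after 1 to 13 doses.
- Two years later (1 March 2025): 717 days. 627/21 = 29.9, so status is wrong after 1 to 30 doses.
- Three years later (1 March 2026): 1,082 days. 992/21 = 47.2, so status is wrong after any number up to 35.

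**The case against.** The best defence is that the wording is loose rather than wrong. A record that lacks only the day still carries its year, so the month can be read as a specific month of a specific year. Start rule b sits directly below and uses the year. That reading is reasonable, and a careful programmer may adopt it. It does not remove the problem, because the end-date rule in the same section states both conditions and so makes literal coding of the start rule a legitimate reading too.

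It can also be said that affected records should be rare. Protocol 8.3.2 collects a start date and time for every AE, and protocol 8.3.9 requires SAE reports within 24 hours. SAP 3.3.6 keeps flags on imputed dates. All of this stands and limits the size of the problem.

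A reader might infer more than the documents support:

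- *Old medications are misclassified.* A drug that stopped before the first dose cannot be moved to the first-dose date, because of the guard. One still being taken gets a wrong start date but stays concomitant: SAP 4.1.8.1 separates prior from concomitant by the stop date.
- *Any AE more than 90 days after the last dose becomes treatment-emergent.* Non-serious AEs are not collected that late under protocol 8.3.1, so this route is essentially limited to SAEs.
- *Every displaced AE changes status.* An AE moved back a year while the participant is still on treatment is treatment-emergent either way.
- *About 1 in 12 partial dates are misclassified.* A chance match of months would give 1/12, about 8%, but only among partial-date records from another year. It counts displaced dates, many of which change no class.

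**Conclusion.** The point holds in a limited form and is minor. Read literally, start rule a gives the wrong status to three kinds of record with a missing start day in the first-dose month of a later year: SAEs starting more than 90 days after the last dose, AEs starting after subsequent anticancer therapy, and medications started more than 90 days after the last dose. In every case where status changed, the error over-counts treatment-emergent events or concomitant medications.

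Efficacy endpoints are untouched, durations are protected by the SAP's own rule, and records from the first-dose year do not change. The conclusion assumes that the rule is coded as written. The documents do not say how many start dates lack a day, so the number of affected records cannot be calculated; it is probably small. The calendar dates above are illustrative, but the mechanism does not depend on them.

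**What to change.** In SAP 3.3.6, limit the exception in start rule a to records where the month and the year both match those of the first dose of study drug; otherwise impute the first of the recorded month. This brings the rule into line with end rule a. It costs one phrase in the SAP and the matching condition in the date-imputation code. It needs no new data and changes no record from the first-dose year.
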